1 LIST OF ABBREVIATIONS AND DEFINITIONS

Abbreviation	Definition
AE	adverse event
AST	Aspartate aminotransferase
CL	cutaneous leishmaniasis
FDA	Food and Drug Administration
HX	History
IND	Investigational New Drug Application
IRB	Institutional Review Board
kDNA	kinetoplast minicircle deoxyribonucleic acid
ML	mucosal leishmaniasis
L.	Leishmania
MRHD	maximum recommended human dose
NDA	New drug application
PI	Principal Investigator
PL	Product Label
PMR	Post Marketing Requirement
US	United States
VL	visceral leishmaniasis
WHO	World Health Organization

2 STUDY SCHEDULE OF ASSESSMENTS

Parameter	Study Time Period				
	Screening	End of Treatment Period	1 Month Post Treatment	3 Months Post Treatment	6 Months Post Treatment
Consent	X				
Demographics (gender/age/weight/race)	X				
Leishmaniasis Hx	X				
Concomitant Diseases	X	X			
Miltefosine treatment	(a)	X			
Clinical Laboratory Tests	X (b,c)	X(b,c)	X (c)	X (c)	X (c)
Concomitant Medications	X	X			
Adverse Events	X	X			
Efficacy		X	X	X	X

(a): Patients may contact the Registry after having been administered at least one dose of miltefosine
 (b): AST and creatinine at screening and end of treatment; white blood cells (WBC), hemoglobin, and platelet count for patients with VL at all time

3 SYNOPSIS

Impavido® (miltefosine) was approved in the United States (US) in March 2014 for the treatment of visceral, cutaneous, and mucosal leishmaniasis due to specified *Leishmania* species. Impavido is the first drug approved in the US for cutaneous or mucosal leishmaniasis, and is the only oral drug worldwide that is generally effective for the leishmaniases.

Since oral miltefosine is administered at 2 capsules for day to patients of 30-44 kg and 3 capsules per day to patients > 44 kg, in each weight bracket, higher weight patients will receive less drug on a mg/kg basis than lighter patients. For example, patients who weigh 45 kg and receive 3 capsules per day will receive 3.3 mg/kg/day whereas patients who weigh 90 kg and receive 3 capsules will receive 2.0 mg/kg/day.

Whether higher-weight US patients will have efficacy rates that are lower on an absolute basis is unknown.

Objective: The purpose of this observational study is to fulfill PMR 2127-4: implement a higher-weight-patient registry for the time period Mar 2015-Mar 2020.

Study Design: This study is a prospective observational study in which patients undergoing treatment for leishmaniasis with Impavido in the US and who weigh > 75 kg can volunteer to provide information about their clinical response to treatment up to 6 months after the start of treatment.

Population: Leishmaniasis patients treated with Impavido who weigh more than 75 kg.

Drug Product:

Drug name: Impavido (50 mg capsules).

Dosing regimen: as per the Impavido Product Label

Study Procedures: Patients who weigh more than 75 kg will become aware of the Impavido Higher-Weight Patient Registry via the Impavido website. By calling [name], the patient will be connected to the Impavido Higher-Weight Patient Registry Coordinating Center. A trained staff member will acquaint the patient with the goals and procedures of the study. If the patient tentatively agrees to participate in the study over the telephone, the patient will be mailed information forms, the Consent/Assent Forms, and the Consent for the patient's physician to release medical information. Receipt of the two signed Consent and/or Assent Forms by the Coordinating Center will signify patient consent. The Coordinating Center will contact the patient's physician at the end of treatment, and at 1, 3, and 6 months after completing treatment, to collect data on efficacy and adverse effects (only during treatment).

Sample Size and Study Duration: Estimated 3-10 patients per year for 5 years.

Outcome Parameters:

Efficacy

Adverse effects

Analysis: Baseline data, compliance to prescribed treatment, and outcomes will be reported for individual patients and for all patients.

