8.2 Concomitant Therapy

All concomitant medications will be recorded on the data form.

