9 PROCEDURES

Parameter	Study Time Period				
	Screening	End of Treatment Period	1 Month Post Treatment	3 Months Post Treatment	6 Months Post Treatment
Consent	X				
Demographics (gender/age/weight/race)	X				
Leishmaniasis Hx	X				
Concomitant Diseases	X	X			
Miltefosine treatment	(a)	X			
Clinical Laboratory Tests	X (b,c)	X(b,c)	X (c)	X (c)	X (c)
Concomitant Medications	X	X			
Adverse Events	X	X			
Efficacy		X	X	X	X

(a): Patients may contact the Registry after having been administered at least one dose of miltefosine
 (b): AST and creatinine at screening and end of treatment;
 (c): White blood cells (WBC), hemoglobin, and platelet count for patients with VL at all time

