9.4 Outcomes

The Impavido Higher-Weight Patient Registry Coordinating Center will contact the patient's physician at the end of the treatment period, and at 1, 3, and 6 months after the end of therapy, and request that the relevant data forms be completed and submitted.

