10 DATA TO BE OBTAINED

10.1 Screening

Demographic Data

Age
Weight
Sex
Race
Prior medications
Geographic area where *Leishmania* infection was acquired
Immune status [normal vs abnormal. If latter, specify disease]

Leishmaniasis History

Site of infection [mark body chart]
Disease parameters
VL : Spleen size
Hemoglobin, platelets, white cell count
ML: Symptoms, Physical status at site of infection
CL : Lesion characteristics at entrance: ulcer, nodule, plaque, scab
Lesion size at entrance: Approximate size [length x width in inches, cm, or finger widths]

Clinical Laboratory Tests

AST, creatinine, and if the patient has VL WBC, hemoglobin, and platelet count

Concomitant Diseases

Concomitant Medications

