10.2 Treatment Data

Miltefosine Treatment Regimen

Daily dose in mg, dose in mg/kg, duration of therapy

Adverse events

Symptoms: gastrointestinal, other
Laboratory parameters (if available)

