10.3 Efficacy Data at 1, 3, and 6 months

- VL : Spleen size
Hemoglobin, platelets, white cell count
- ML: Symptoms, physical status at original site of infection
- CL : Lesion characteristics: ulcer, nodule, plaque, scab
Lesion size: Approximate size [length x width in inches, cm, or fingerwidths]

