13.3 Data Editing and Control

Data received at the Impavido Higher-Weight Patient Registry Coordinating Center will be reviewed prior to being entered into the main study database. If incomplete or inaccurate data are found, a data clarification request will be forwarded to the patient and/or patient's physician for a response.

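### Efficacy is followed to month 6, but the protocol asks for no record of further antileishmanial treatment after Impavido ends

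*Protocol*

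**What the plan says.** - **Contacts.** Section 9.4 has the physician contacted "at the end of the treatment period, and at 1, 3, and 6 months after the end of therapy". The synopsis (section 3, Study Procedures) says what these contacts are for: "at 1, 3, and 6 months after completing treatment, to collect data on efficacy and adverse effects (only during treatment"). The restriction to the treatment period qualifies adverse effects; medications are not mentioned.
- **Schedules (sections 2 and 9).** The row "Concomitant Medications X X" has its two marks under Screening and End of Treatment. The Efficacy row is marked at End of Treatment and in all three later columns.
- **Section 8.2.** "All concomitant medications will be recorded on the data form". No period is stated.
- **Section 10.1.** Prior medications and "Concomitant Medications" are screening items.
- **Section 10.2.** The only drug item is "Miltefosine Treatment Regimen".
- **Section 10.3 (months 1, 3 and 6).** Only disease signs are listed: spleen size and blood counts for VL, symptoms and physical status for ML, and for CL "Lesion characteristics: ulcer, nodule, plaque, scab" plus lesion size.
- **Section 13.3.** "If incomplete or inaccurate data are found, a data clarification request will be forwarded" to the patient or physician.

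Re-treatment, rescue or other antileishmanial therapy after miltefosine is not mentioned anywhere.

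**The concern.** Section 4.4 gives the scientific purpose as informing the relation between lower mg/kg daily doses and efficacy. For that, a status recorded at month 3 or 6 has to be attributable to the Impavido course. Care stays with the patient's own physician (section 12.3), and nothing in the protocol restricts further treatment, so some patients who fail may receive another drug or a second course within the follow-up period.

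If such a patient then improves, the later efficacy record looks like a response to Impavido. The error has one direction: it can only make efficacy at low mg/kg doses look better. A re-treated patient who still shows disease causes no such error. If the forms follow the protocol text, the problem cannot be repaired at analysis, because an analysis plan can classify recorded re-treatment but cannot supply information that was never requested.

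**Working it through.** The protocol states no figure on this point, so there is none to reproduce. The check is a comparison of sections, followed by arithmetic for scale.

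**Step 1. What each time point collects (schedules in sections 2 and 9)**

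| Row | Screening | End of treatment | Month 1 | Month 3 | Month 6 |
|---|---|---|---|---|---|
| Concomitant medications | yes | yes | no | no | no |
| Miltefosine treatment | footnote (a) | yes | no | no | no |
| Efficacy | no | yes | yes | yes | yes |

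Efficacy is marked in 4 of 5 columns and concomitant medications in 2 of 5. All three post-treatment columns collect efficacy, and none collects any treatment.

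**Step 2. Whether another section fills the gap**

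- Section 8.2 is general and undated. The schedules place its item at screening and end of treatment only, and a drug started after miltefosine ends is not clearly concomitant with it.
- Sections 10.1 and 10.2 cover screening and the miltefosine course. Section 10.3 has no treatment item.
- The query in section 13.3 is triggered by incomplete or inaccurate data. A form that never asked about re-treatment is neither, so this is not a stated route to the information.

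**Step 3. Registry size (section 3, Sample Size and Study Duration)**

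- 3 per year × 5 years = 15; 10 per year × 5 years = 50.
- Effect of one misattributed patient on the overall response percentage: 1/15 = 6.7 points; 1/50 = 2.0 points.

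**Step 4. Which dose rows of section 4.2.5 are relevant**

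- Labelled regimen at 45 kg or more (section 4.2.4): 3 × 50 mg = 150 mg/day.
- 150/75 = 2.0 mg/kg/day, so every patient above 75 kg on that regimen receives less than 2.0 mg/kg/day.
- This matches the lowest row of Table 1 (VL, below 2 mg/kg) and overlaps the lowest row of Table 2 (CL, 1.7-2.2 mg/kg).

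**Step 5. Failures if those rows applied (assumption)**

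| Source | Failure share | Among 15 | Among 50 |
|---|---|---|---|
| VL, Table 1 | 12/94 = 12.8% | 15 × 0.128 = 1.9 | 50 × 0.128 = 6.4 |
| CL, Table 2, as printed | 27.9% | 15 × 0.279 = 4.2 | 50 × 0.279 = 14.0 |
| CL, Table 2, on the printed N | 12/38 = 31.6% | 15 × 0.316 = 4.7 | 50 × 0.316 = 15.8 |

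Both CL shares are shown because the printed percentage does not follow from the printed N. The range is 1.9 to 4.7 failures among 15 patients and 6.4 to 15.8 among 50. These are failures, not re-treatments. The share of them re-treated, improved by month 6 and unrecorded is not given.

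**The case against.** The strongest reply is that the gap may not exist in practice. Section 8.2 promises that all concomitant medications are recorded, the Coordinating Center prepares the forms (section 14.3), and a question on other treatment is often set at form level. A physician may also volunteer the information. This stands as a limit on the finding, because the forms are not shown. It does not remove the finding: the protocol specifies the data, and its schedules narrow section 8.2 to two time points.

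Second, the protocol fixes no month-6 responder rule. By-subject listings are promised (section 11.6), and with 15 to 50 patients a course of worse then better could be read directly. This reduces the risk in part. A listing may show an earlier failure but not why the patient improved, and relapse, re-treatment and improvement could all fall between the month 3 and month 6 contacts.

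Third, the study is descriptive, and the FDA request quoted in section 4.3.2 does not name post-treatment therapy. That is true, and the omission contradicts nothing in that request. But a description of efficacy still has to be attributable to the drug described, and section 4.4 sets the wider aim of relating dose to efficacy.

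Fourth, the failure counts are not a measure of bias. They treat the registry as all VL or all CL and give no figure for ML. Patients above about 88 kg (150/1.7 = 88.2) fall below the lowest CL row. This stands: the counts only show how many patients could be concerned under the assumption.

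**Conclusion.** The concern holds. As written, the protocol follows efficacy for six months after treatment without asking about further antileishmanial treatment, so improvement after re-treatment could not be told from a response to Impavido.

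The size of any overstatement cannot be estimated. Assuming the lowest-dose failure shares in section 4.2.5 carry over, it runs from no patients up to about 2 to 5 of 15, or 6 to 16 of 50. An actual error requires that re-treatment occurs, is followed by improvement at a later contact, and is neither asked for on the forms nor volunteered.

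Confidence is medium because the forms are not shown. The change is worth making: it is cheap, and the missing information may be hard to recover afterwards.

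**What to change.** 1. Add one item to section 10.3 and to the month 1, 3 and 6 columns of both schedules: *any further antileishmanial treatment since last contact (drug, date, reason)*.
2. State in section 8.2 the period over which medications are recorded, so that it agrees with the schedules.
3. Name the item in the synopsis sentence describing the contacts.
4. In the by-subject listings, flag outcomes observed after re-treatment.

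The cost is one extra question on forms already requested from the physician, plus short wording changes. It needs no extra visit or contact, concerns data capture only and sets no clinical rule. If the forms already carry the question, only the wording changes and the listing flag remain.

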4 INTRODUCTION AND RATIONALE

4.1 Leishmaniasis

Infection of the macrophages of the skin, mucosal membranes, and visceral reticuloendothelial system with *Leishmania* gives rise to the major forms of leishmaniasis: cutaneous, mucosal, and visceral disease.

According to the World Health Organization (WHO), *Leishmania* infection is endemic in 98 countries or territories with a yearly incidence of 0.5 million cases of visceral leishmaniasis (VL) and 1.5 million cases of cutaneous leishmaniasis (CL) (WHO 2010).

VL (Kala-azar) -- infection of the liver, spleen, and bone marrow-- presents with fever, hepatosplenomegaly, and pancytopenia. The majority of VL occurs in the Indian subcontinent. Approximately 30% of the world's cases occur in Africa especially Sudan, Ethiopia, and Kenya; there is also a focus of disease in Brazil. The main species causing VL are *Leishmania (L). donovani* in India and Africa, *L. infantum* in Europe and the Mediterranean, and *L. infantum chagasi* in the New World.

In VL, Sudden onset of fever with rigor and chills herald the onset of illness, which may subside to recur again. Splenomegaly soon follows and may become remarkable. Hepatomegaly and lymphadenopathy are other clinical features, though the latter is rare. Anemia is universal and may be quite severe leading to weakness, fatigue and heart failure. Thrombocytopenia and subsequent bleeding episodes such as epistaxis, intestinal bleeding, and retinal hemorrhages are not uncommon. Concurrent illnesses including pneumonia, herpes zoster, tuberculosis, amebic or bacillary dysentery, boils, and scabies are common. VL and coinfection with HIV or other immunocompromising diseases is increasingly a serious health threat.

CL generally presents as a papule that enlarges to a nodule and if it ulcerates, does so over 1 to 3 months. CL lesions are often located at exposed areas of the skin (face, arms, legs), either as single or as multiple lesions. Lesions can develop in anybody who intrudes into an endemic region and gets bitten by an infected sand fly. In recent years, industrialized nations have become more aware to the problem due to increasing numbers of imported cases either by military personnel or travelers. In the New World from the Texas-Mexico border down through South America to the level of the Tropic of Capricorn, ulcerative lesions are most common. In the Old World (the Mediterranean, North and Sahelian Africa, the Middle East, the Indian subcontinent, and Central Asia), most lesions are papules, nodules, or nodule-ulcers. The primary species causing CL are diverse: *L. mexicana*, *L. amazonensis*, *L. viannia (v) panamensis*, *L. (v) braziliensis*, *L. (v) peruviana*, and *L. (v) guyanensis* in the New World and *L. major*, *L. tropica*, *L. aethiopica*, and *L. infantum* in the Old World.

[figure not shown]
Mucosal disease (ML) in the New World may result from dissemination of cutaneous organisms (particularly *Leishmania* species of the subgenus *Vianna*: *L. (v). braziliensis*, *L.(v). guyanensis* and *L.(v) panamensis*) to the nares, nasal septum, palate, pharynx, and larynx. Mucosal disease causes a progressive destruction of the mucosa, the cartilage and bones of nose and pharynx, leading to a severe mutilation of the face. ML can be lethal by aspiration pneumonia or other

complications. Classic ML occurs months to years after healing of CL, but ML can also occur virtually simultaneously with CL. Recently, it was shown that asymptomatic infection of the mucosal membranes is common for CL patients infected with members of the *L. viannia* subgenus. Two patients with ML and 26 patients with CL due to *L. v. panamensis*, *L.v. guyanensis*, and *L.v. braziliensis* had *Leishmania* kinetoplast minicircle deoxyribonucleic acid (kDNA) examined in mucosal tissues. kDNA was amplified from swab samples of nasal mucosa from 14 (58%) of 24 patients, tonsils from 13 (46%) of 28 patients, and conjunctiva from 6 (25%) of 24 patients. Although the reason that initially asymptomatic infection converts to clinical disease is unknown, cutaneous infection with any of these 3 species has to be regarded as leading to mucosal infection and potentially to mucosal disease with its possibly fatal outcome.

4.2 Miltefosine

4.2.1 Structural Formula

Miltefosine (hexadecylphosphocholine) is a phosphatidylcholine analogue. The structural formula of miltefosine is:

4.2.2 Worldwide Registration

The drug was registered in India in 2002 and in Germany in 2004 to treat visceral leishmaniasis. Impavido was registered in Columbia in 2005 to treat visceral and cutaneous leishmaniasis, and post-2005 to treat CL (and by extension ML) in many other countries in the Americas.

4.2.3 US Registration and Indications [Impavido PL, 2014]

On 19 Mar 2014, miltefosine (trade name Impavido®) was approved in the US for treatment of visceral, cutaneous, and mucosal leishmaniasis due to specific species of *Leishmania* (Impavido PL, 2014).

- Visceral leishmaniasis (VL) due to *Leishmania donovani*
- Cutaneous leishmaniasis (CL) due to *Leishmania braziliensis*, *Leishmania guyanensis*, and *Leishmania panamensis*
- Mucosal leishmaniasis (ML) due to *Leishmania braziliensis*

4.2.4 Recommended Dosage [Impavido NDA, 2014]

Each IMPAVIDO capsule for oral use contains 50 mg miltefosine.

Administer with food to ameliorate gastrointestinal adverse reactions.

30 to 44 kg: one 50 mg capsule twice daily for 28 consecutive days.

45 kg or greater: one 50 mg capsule three times daily for 28 consecutive days.

4.2.5 Higher-Weight-Patient Considerations

Since oral miltefosine is administered at 2 capsules for day to patients of 30-44 kg and 3 capsules per day to patients > 44 kg, in each weight bracket, higher patients will receive less drug on a mg/kg basis than lighter patients. For example, patients who weigh 45 kg and receive 3 capsules per day will receive 3.3 mg/kg/day whereas patients who weigh 90 kg and receive 3 capsules will receive 2.0 mg/kg/day.

In developmental studies for both VL and CL, there appeared to be a trend towards less efficacy with a lower mg/kg/day dose.

For VL, the cure rate in patients receiving < 2 mg/kg/day (86%) was less than the cure rate in higher mg/kg/day patients (Table 1).

Table 1: Cure Rate by Dose Level in VL Studies in India (mg/kg/day)

(Daily)Dose per kg body weight	Final parasitological cure, ITT population ^a						All
	No		Yes		Missing/ not assessable		
	n	%	n	%	n	%	n
<2 mg	12	12.8	81	86.2	1	1.1	94
2.0-2.4 mg	12	6.3	174	92.1	3	1.6	191
2.5-2.9 mg	3	1.3	213	95.5	7	3.1	223
3.0-3.9 mg	2	2.2	89	96.7	1	1.1	92
≥4 mg	3	4.3	66	95.7	0	0	69
All	32	4.8	623	93.4	12	1.8	667

For CL, there was a trend towards a lower cure rate in patients receiving a lower mg/kg/day dose (Table 2).

Table 2: Final Cure Rates with respect to Miltefosine Dose: Integrated Analysis of CL Studies 3168, Soto, Z020a, Z020b

Dose Group (mg/kg/day)	N	Failed N (%)	Cured N (%)
1.7-2.2	38	12 (27.9)	26 (60.5)
2.3-2.8	128	24 (17.8)	104 (77.0)
2.9-3.3	27	6 (22.2)	21 (77.8)

Whether higher-weight US patients will have cure rates that are low on an absolute basis is unknown.

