4.4 Rationale for Protocol

In an operational sense, the purpose of this protocol is to fulfill post-marketing requirement 2127-4 in accord with the specifics of the information request of 24 Jan 2014.

In a scientific sense, the purpose of this protocol is to provide as much data as possible on the possible relationship of lower mg/kg daily doses of miltefosine and efficacy.

For these purposes, a Higher-weight Patient Registry will be instituted and maintained from March, 2015 to March, 2020.

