7.2 Inclusion Criteria

To be eligible for the study, the following must be answered “YES”:

1. Did the subject give consent to collect data from her or her physician?
2. Was the subject treated for leishmaniasis with miltefosine?
3. Does the subject weigh more than 75 kg?

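### Does the 90 kg dose example, which does not match the protocol's own capsule count, undermine the registry's dose-efficacy purpose?

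*Protocol*

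**What the plan says.** Section 4.2.5 explains why heavier patients receive less drug per kilogram and gives two examples. At 45 kg, three capsules are said to give 3.3 mg/kg/day. For the heavier patient it says that "patients who weigh 90 kg and receive 3 capsules will receive 2.0 mg/kg/day". The Synopsis repeats both examples.

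Section 4.2.4 supplies the components: "Each IMPAVIDO capsule for oral use contains 50 mg miltefosine" and "45 kg or greater: one 50 mg capsule three times daily for 28 consecutive days". The Synopsis sets the registry's regimen: "Dosing regimen: as per the Impavido Product Label". Section 7.2 asks for entry: "Does the subject weigh more than 75 kg".

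Section 4.2.5 then reports that in visceral disease (VL) "the cure rate in patients receiving < 2 mg/kg/day (86%) was less than the cure rate in higher mg/kg/day patients" (Table 1), and describes a similar trend for cutaneous disease (CL) in Table 2, whose lowest dose band is 1.7-2.2 mg/kg/day. Section 4.4 gives the scientific purpose of the protocol as "to provide as much data as possible on the possible relationship of lower mg/kg daily doses of miltefosine and efficacy".

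**The concern.** The 90 kg figure cannot be obtained from the capsule strength and count in section 4.2.4. It is also the only worked example for a patient heavy enough to enter the registry, and the error crosses a line that the text then uses. At the printed 2.0, a 90 kg patient with VL belongs to Table 1's 2.0-2.4 band (cure 92.1%). By the capsule count, the same patient belongs to the band below 2 (cure 86.2%).

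A reader who trusts the example could think that the registry spans 2.0 mg/kg/day, with lighter subjects at or above it and heavier ones below. On the label regimen no subject above 75 kg reaches 2.0. The registry alone could then not show a difference across that line. If the scientific purpose in section 4.4 depended on such a contrast, the protocol would be promising something that it cannot deliver.

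The two background tables that support the rationale also contain figures that do not agree with each other. That raises the question of whether the trend they are cited for is real.

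**Working it through.** **Dose examples.** Inputs: 50 mg per capsule and three capsules daily (section 4.2.4). Formula: mg/kg/day = capsules x 50 / weight.

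- 45 kg: 150/45 = 3.33. Printed 3.3, so it reproduces and the method is the protocol's own.
- 90 kg: 150/90 = 1.67. Printed 2.0, so it does not reproduce. Ratio 2.0/1.67 = 1.20.
- Working back from 2.0 at 90 kg: 2.0 x 90 = 180 mg, or 180/50 = 3.6 capsules, which is not a whole number.
- The same formula gives 2.0 at 75 kg (150/75). The document does not show whether the weight or the mg/kg value was mistyped.

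**Range covered by the registry.** At 150 mg/day and weight above 75 kg:

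- 76 kg: 150/76 = 1.97
- 90 kg: 1.67
- 120 kg: 150/120 = 1.25

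All on-label subjects are below 2.0, but mg/kg still varies among them. This follows from the weight limit and the fixed daily amount, whatever the example says.

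**Table 1 (VL), 2.0-2.4 row.**

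- Cells: 12 + 174 + 3 = 189; printed total 191.
- 174/189 = 92.1%, as printed; 174/191 = 91.1%.
- Row totals: 94 + 189 + 223 + 92 + 69 = 667, the printed overall total. With 191 the sum is 669.
- All other rows reproduce. On either total the cure rate in this row exceeds the 86.2% (81/94) in the band below 2.

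**Table 2 (CL).**

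| Band (mg/kg/day) | Printed N | Cured | Printed cure % | Cure % on printed N | Denominator that fits the printed % |
|---|---|---|---|---|---|
| 1.7-2.2 | 38 | 26 | 60.5 | 26/38 = 68.4 | 26/43 = 60.5 |
| 2.3-2.8 | 128 | 104 | 77.0 | 104/128 = 81.25 | 104/135 = 77.0 |
| 2.9-3.3 | 27 | 21 | 77.8 | 21/27 = 77.8 | 27 |

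The failure percentages fit the same denominators: 12/43 = 27.9% and 24/135 = 17.8%. In each row the printed N equals failed plus cured. The percentages may therefore count 5 and 7 further patients (43 - 38 and 135 - 128) without an assessed outcome; the document does not say so. The lowest band has the lowest cure rate on either basis. On the printed N the middle band is slightly above the top one, but the statement about lower doses rests on the lowest band.

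**Where the figures are used.** Eligibility (section 7.2) depends on weight, consent and treatment. Section 10.2 collects each subject's daily dose in mg and in mg/kg. Section 11.5 reports exposure, including mg/kg, by subject and in summary. Section 11.1 has no hypothesis and no sample size calculation, and section 11.3 plans descriptive statistics. None of these draws on the 90 kg example or on either table.

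**The case for a change.** The strongest case for acting is that this is more than a misprint. The example illustrates the premise of the study, appears twice, and puts a 90 kg patient on the wrong side of the VL line. The protocol never says that its whole on-label population lies below 2.0 mg/kg/day, or that subjects heavier than about 88 kg (150/1.7 = 88.2; about 91 kg if 1.65 is rounded up, 150/1.65 = 90.9) lie below the lowest CL band in Table 2. One sentence in section 4.4 stating the range would cost little and would tell readers of the yearly and final reports that any contrast with higher doses must come from outside the registry.

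The arithmetic in this case stands in full. The inference to the design does not:

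- The range below 2.0 comes from the 75 kg threshold in the regulator's requirement (sections 4.3 and 4.3.2) together with label dosing. Reconciling the example would alter no enrolled subject and no summary.
- Section 4.4 speaks of a possible relationship between lower doses and efficacy and promises no comparison across 2.0. The open question at the end of section 4.2.5 is whether cure rates in heavier US patients are low in absolute terms. Subjects below 2.0 can answer that without others above it.
- The 2.0 line belongs to VL only. For CL, both 2.0 and 1.67 (1.7 to one decimal) fall in Table 2's lowest band, so the example does not move the patient out of the low-cure group there.
- The reports will show each subject's actual mg/kg dose, so the true range will be visible without an added sentence.

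A count of subjects misplaced by the example would need a weight distribution that the protocol does not give, and no analysis would use it.

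**Conclusion.** The protocol contradicts its own figures in three background places: 2.0 against 1.67 mg/kg/day at 90 kg on three capsules (Synopsis and section 4.2.5 against section 4.2.4); a Table 1 row total of 191 against cells summing to 189; and Table 2 percentages on 43 and 135 beside N of 38 and 128. The passages on weight, capsule count and mg/kg must be reconciled, and the table totals and denominators made consistent. No view is taken here on which dosing figure is right.

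These are clerical slips. They affect no enrolled subject, data item or planned summary, and the direction of the background trends that motivate the registry holds on either set of figures. The statement that all registry subjects are below 2.0 mg/kg/day assumes label dosing at 150 mg/day, as the Synopsis states; section 7.2 does not itself require it. The reading of the Table 2 denominators as including patients without an assessed outcome is likewise an assumption, and the conclusion does not depend on it. The registry can still do what section 5 and the regulator's requirement ask, which is to describe outcomes in patients above 75 kg. No change to the design, data collection or analysis follows.
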